Study Protocol

Title: Check It! 2.0: Positive Psychology Intervention for Adolescents with T1D

NCT Number: NCT02984709

Date: 10/12/2016

Research, Activities, Procedures, and Schedule of Events for Study Participants

Please check all that apply to your study and describe each below.

- Behavioral Observation
- Randomization
- Blinding
- Surveys, Interviews, Questionnaires
- Document and Artifact Collection
- Deception, Withholding or Postponing Medications/Treatments, or Imposing other Restrictions
- Audio/Video Recording
- Sham Procedure
- Specimen/Data Collection and/or Storage

DATA COLLECTION, STORAGE OF DATA/SPECIMENS, AND/OR ISSUES OF CONFIDENTIALITY - Describe the procedures that will be utilized to protect the privacy of the research participant. Include who will have access to the research information (for example, video/audio recordings, discovering information about the participant that could be harmful if released such as mental illness, genetic information, sexual preference, drug abuse, etc.) and where it will be stored.

All study documents (consent/assent forms, questionnaires) will be stored electronically in REDCap and will be secured with only study personnel having access to a unique username and password.

Describe how the confidentiality of participants' data will be assured. Include a description of any issues specific to the study that might increase the risk of breach of confidentiality. Describe how codes will be generated if codes are used to protect identities, and who will have access to such codes. If a certificate of confidentiality will be provided, include the name of the person holding the certificate. Describe the final disposition of research data when the study is concluded (e.g., will information be destroyed, will the PI maintain the information indefinitely, etc.).

Participants will be identified with an ID number; names will not be included on any data. Questionnaire data will be shredded after the completion of the study. All study documents will be kept for at least 6 years following the completion of the study. After the 6 year deadline, all data related to this study will be destroyed appropriately

RANDOMIZATION - Describe the randomization process (who will randomize, how will randomization be determined, etc.)

Participants will be randomly assigned to one of two conditions: Positive Psychology Intervention - Text-Messaging (n = 24 adolescent-caregiver dyads), Attention Control - Education (n=24 adolescent-caregiver dyads). A computer program will generate the randomization scheme in 12 blocks of 4. After

consent/assent is obtained, and the participants have completed baseline data, the RA will reveal to which condition he/she was assigned.

SURVEYS, INTERVIEWS, AND QUESTIONNAIRES - If surveys, interviews or questionnaires will be used as part of this study, indicate who will conduct the survey, interview or questionnaire and his/her qualifications. In addition, describe the setting and mode of administering the instrument (e.g., by telephone, one-on-one, group, etc.) and attach a copy of the instrument.

This study is a randomized, controlled trial composed of two conditions: Positive Psychology Intervention - TextMessaging (n = 24 adolescent-caregiver dyads) and Attention Control - Education (n=24 adolescent-caregiver dyads). At the beginning of the study, participants will be asked if they have a cell phone. If a participant does not have a cell phone (estimated at 10% of eligible adolescents), a basic cell phone and plan will be assigned to him/her for the active phase of the study (3 months). In order maximize the likelihood of participation, adolescents in all conditions will be asked the best days/times to contact them. Furthermore, the participants are asked to bring their glucose meters at each of the follow-up visit, to help track the effectiveness of the intervention, by obtaining number of blood glucose checks over the previous week. In addition, all adolescent participants will be required to complete a health behavior contract. This contract acknowledges that the participants agree and are committed to making a positive change in their lives by being proactive in their diabetes management. The contract states that the behavior that they are committing to do (i.e., BGM), when they will do it, and how often they will perform the target behavior.

For adolescents randomized to the Positive Psychology Intervention - Text Messaging group, the RA will instruct them to use the following empirically-validated exercises to induce positive affect :

1) Gratitude: Adolescents will be told that research shows that feeling happy helps people to handle challenges in their lives. We will ask them, "what are some small things that make you feel good, even for a few minutes (e.g., hearing your favorite song, finding the perfect pair of jeans. We will instruct them to do the following exercise: "As you go through your day, notice the small things that make you feel good and take a moment to enjoy them." Reminder messages will be sent through text messages.

2) Self-Affirmation (positive values): Adolescents will be asked to select from a list of positive values that are important to them (e.g. family, athletic ability, friendships). They will be instructed to think about the positive value when they are in a situation that makes it hard to check their blood sugar. Reminder messages will be sent through text messages.

3) Parental Affirmation: We will take the focus of parent-child communication away from diabetes management by asking caregivers to provide weekly positive affirmations to their adolescents, focused on non-diabetes strengths (e.g., "I heard you practicing your guitar - sounded great!" or "I had a great time when we _____.") Caregivers will receive weekly reminders via text message. Parents will be asked to respond back that they have successfully sent a positive affirmation to their child by texting the research team "yes".

4) Gifts: For those in the Text-Messaging Condition, an Amazon gift card (valued at \$5.00) will be sent via text (the redemption code will be sent via SMS to participants). Gifts will be sent every 2 weeks for 8 weeks (Weeks 2, 4, 6, 8). All adolescents will be given developmentally-appropriate diabetes education material at the time of enrollment (see attached for Educational Materials).

In addition, on weeks 2, 4, 6, 8, the Positive Affect Negative Affect Scale - Children (Brief Version) will be administered by SMS to all adolescents. This brief measure of affect consists of 10 questions, which will take less than 5 minutes to complete, and data will be stored in a secure online database.

For all participants that complete the study, an exit interview and evaluation will be administered at the final data collection (3 months) The series of questions will help the research investigators determine the feasibility and acceptability of the intervention and provide insight into areas of improvement (included as redcap survey attachment - teen).

A trained RA (Master's or Bachelor's level) will administer the survey to the participants on a study iPad at the diabetes clinic in a private space at each of the follow-up visits. The surveys are composed of 6 sections for the adolescents and 4 sections for caregivers.

Each section has specific directions and consists of multiple questions/choices pertaining to a particular measure. The measures are designed to evaluate the relationship between adherence and coping strategies in teens with type 1 diabetes.

The measures included on the adolescent's survey include:

Patient Health Questionnaire (PHQ-9): as a measure of current depressive symptoms. The PHQ consists of 9 items, and higher scores indicate higher current levels of depression, with a score of 11 or higher suggesting clinical levels of depression, with sensitivity of 89.5% and specificity of 77.5% for detecting major depression. If an adolescent endorses the item "Thoughts that you would be better off dead or of hurting yourself in some way?" the PI, a licensed clinical psychologist, will screen the adolescent to determine if emergency care is needed. Positive psychology interventions may have a larger effect in depressed individuals; therefore, it is important to measure depressive symptoms.

Positive and Negative Affect Scale for Children (PANAS-C): will be used to measure adolescents' affect. This measure consists of two 5-item scales to measure positive affect (i.e., joyful, cheerful, happy, lively, proud) and negative affect (i.e., miserable, mad, afraid, scared, sad). Respondents are asked to rate on a 5-point scale the extent to which they have experienced each particular emotion within the last week. This scale has demonstrated validity and reliability similar to that of the full scale PANAS-C and has been used in other studies in pediatric populations with mobile phone data collection

Responses to Stress Questionnaire (RSQ): will be used to measure coping style in response to diabetes-related stressors. The first 10 items of the measure list stressors tailored to reflect topics shown to be stressful for adolescents with T1D, followed by 57 items asking how the individual responds to these stressors. The RSQ has been shown to have good reliability and validity, including internal consistency (alphas form .73 to .85) and construct validity as reflected in results of confirmatory factor analyses. The

three coping factors on the RSQ will be used in the proposed study: primary control engagement coping (problem solving, emotional modulation, emotional expression), secondary control engagement coping (positive thinking, cognitive restructuring, acceptance, distraction), and disengagement coping (avoidance, denial, wishful thinking). To control for response bias and individual differences in base rates of item endorsement, proportion scores (i.e., type of coping over total coping) will be used for all analyses.

Self-Care Inventory (SCI-C): assesses key elements of the treatment regimen for T1D: diet, exercise, blood glucose monitoring, insulin administration, and attending medical appointments. The wording applies to various insulin regimens (i.e., pump and injections). It has been shown to have good reliability and validity. The Parent and Child versions will be used to measure adherence. The Overall Care scale and Blood Glucose Regulation subscales will be used in data analyses.

Pediatric Quality of Life (PedsQL): diabetes-specific measure will be used. Following recent recommendations, the 28 items will be summed to create a total diabetes-related quality of life score. Higher scores reflect better quality of life.

Revised Diabetes Family Conflict (DFC-C): will be used to evaluate conflict related to treatment management. Diabetes conflict is measured on 15 items regarding diabetes regimen activities, including BGM, and higher scores indicate more conflict. Good reliability has been established.

The measures included on the caregiver's survey include:

Demographic information: a questionnaire will be completed by the caregiver including information such as race/ethnicity, marital status, age and sex of child with T1D, caregiver's relationship to the child (i.e., biological parent, grandparent), adults living in the home, and screening information about the overall health status of the child. SES will be measured with separate items for parental income, occupation, and years of education.

Revised Diabetes Family Conflict Scale (DFC-P): will be used to evaluate conflict related to treatment management. Diabetes conflict is measured on 15 items regarding diabetes regimen activities, including BGM, and higher scores indicate more conflict. Good reliability has been established.

Self-Care Inventory (SCI-P): The Parent versions will be used to measure adherence (see above).

The Center for Epidemiologic Studies of Depression Scale (CES-D): will be used as a brief, self-report measure of depressive symptoms in caregivers. This measure is widely used with both clinical samples and community surveys, with excellent reliability (alphas ranging from .85-.90). Maternal depression has been linked with poorer glycemic control and lower quality of life in youth with T1D; therefore, it may be an important covariate to include in analyses.

In addition we will collect Glycosylated Hemoglobin (A1C) from the adolescent's medical chart and blood glucose monitoring data by downloading the adolescent meter. Glycemic Control: Glycosylated Hemoglobin (A1C), an objective criteria of metabolic control over the prior 8-12 weeks, is measured

quarterly in patients with T1D. Analyses will be performed using the Bayer Diagnostics DCA2000® machine.

Blood Glucose Monitoring Frequency will be obtained via home glucose meter download at the time of study enrollment (if possible) and again at 3 month clinic visit. This method has been used successfully as a measure of adherence in other studies. Incentives will be provided to increase the likelihood of adolescents bringing all of their glucose meters to their clinic visits (\$10 per follow-up visit). The survey will take approximately 30 minutes to complete.

DOCUMENT AND ARTIFACT COLLECTION - Describe any documents or other artifacts (e.g., student written assignments, EKG report, x-rays, etc.) that are to be collected and used as part of the research study.

Participant's A1C will be collected from their medical chart at enrollment and at the the 3 month follow-up visit. Additionally, we will be collecting numbers from the participants blood glucose meter at enrollment and at the the 3 month follow-up visit.

AUDIO/VIDEO RECORDING - Describe how the audio/video recordings will be stored, as well as how they will be disposed of when this research is complete. Describe how the participant's confidentiality will be maintained.

The participants will be administered an exit interview and evaluation that will be audio recorded. Laptops that have recording capabilities will be utilized to record the interviews. Interviews will be saved using the participant's ID number on a secure drive that only study personnel will have access to. Participant confidentiality will be maintained because no names will be used; only participant ID number will be used for identification.

Will the PI create a repository at VU/VUMC with any of the specimens and/or data for future use?

Yes

No

If all of your study is minimal risk, please indicate the categories that it fits 45 CFR 46.110 or 21 CFR 56.110:

N/A: Study is greater than minimal risk or Standard

(F)(1) Drugs or devices where no IND/IDE is required

(F)(2) Collection of blood by stick or venipuncture

(F)(3) Prospective collection of specimens by non invasive means

(F)(4) Collection of noninvasive data through routine clinical practice

(F)(5) Research on materials that have been collected for non research

(F)(6) Collection of data from voice, video, digital or image recordings

(F)(7) Research on individual or group characteristics (surveys)

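### Does the sentence on shredding questionnaire data put the self-report outcomes at risk?

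*Protocol*

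**What the plan says.** The Protocol section on data collection, storage and confidentiality makes four statements about what happens to the records:

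- On scope and medium: "All study documents (consent/assent forms, questionnaires) will be stored electronically in REDCap".
- On questionnaires: "Questionnaire data will be shredded after the completion of the study".
- On retention: "All study documents will be kept for at least 6 years following the completion of the study".
- On final disposal: "After the 6 year deadline, all data related to this study will be destroyed appropriately".

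The section on surveys, interviews and questionnaires says how the data arise. A research assistant "will administer the survey to the participants on a study iPad at the diabetes clinic". In weeks 2, 4, 6 and 8, "the Positive Affect Negative Affect Scale - Children (Brief Version) will be administered by SMS to all adolescents", and for that measure "data will be stored in a secure online database". The same section makes clear that questionnaire scores are analysis variables; for the Self-Care Inventory, for example, "The Overall Care scale and Blood Glucose Regulation subscales will be used in data analyses".

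**The concern.** Questionnaires are expressly counted as study documents, so the retention sentence covers them for at least 6 years. The sentence just before it gives questionnaire data a disposal rule of their own, tied to the same event (study completion), with no waiting period and no restriction to paper. Taken literally, the same records are to be both kept and destroyed.

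The questionnaires carry most of what the trial measures: affect, coping, self-reported adherence, diabetes-related quality of life, family conflict and depressive symptoms. Several scores depend on item-level records, such as the coping proportions built from 57 response items and the quality-of-life total summed over 28 items. If those records were erased, a scoring error found later could not be corrected and a published result could not be verified. Erasure cannot be undone, which is why a careful reader stops at this sentence.

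**Working it through.** The point involves no figure that can be recomputed, so the check sets the sentences side by side.

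**1. Is there a conflict?** Yes, on the face of the text. Questionnaires belong to the study documents, study documents are kept at least 6 years, and questionnaire data are shredded after completion with no interval given. The text says *after* completion, not *at* completion. A retention time of 0 years is therefore an inference; no sentence states it.

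**2. What could the shredding act on?** Shredding is ordinarily a paper process. The Protocol describes no paper questionnaire: the clinic surveys are entered on an iPad, the interim affect scale comes by text message into an online database, and study documents sit in REDCap. If incidental paper exists, destroying it leaves the electronic record whole. If none exists, the sentence has nothing to act on and reads like leftover form wording. Data are lost only if someone applies the sentence to the database.

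**3. Do the neighbouring sentences decide between readings?** Largely. The final sentence of the section deals with all data of the study, which includes questionnaire data, and puts their destruction after the 6 years. Two readings fit the whole paragraph:

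- paper is shredded, and the electronic record is kept 6 years and then destroyed; or
- shredding names the method, and 6 years sets the time.

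Both preserve the electronic questionnaire data for the full period.

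**4. How much is involved on the worst reading?**

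- Dyads: 24 + 24 = 48.
- Adolescent instruments: PHQ-9, PANAS-C, RSQ, SCI-C, PedsQL and DFC-C, which makes 6.
- Caregiver instruments: DFC-P, SCI-P and CES-D, which makes 3, plus the demographic form.
- Outside the questionnaires: A1C from the chart, the glucose-meter downloads and the audio-recorded exit interview, which informs feasibility and acceptability.

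So it would be wrong to say that everything except A1C and meter data is exposed. Nor is every questionnaire plainly an outcome: the caregiver depression scale is introduced as a possible covariate, and the adolescent depression measure is justified by a possibly larger effect in depressed participants.

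**5. When would the loss occur?** After the study is complete. The Protocol does not define completion, but nothing in it places disposal before analysis, and it states that questionnaire scores will be analysed. Even on the worst reading, what would go is later audit and re-scoring.

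**The case for a change.** The best case for a change is that neither harmless reading is written down. The sentence says questionnaire data, not paper copies, and it answers a form prompt about the final disposition of research data. On the paper-only reading it governs material the Protocol never describes, and any paper that did exist would itself be a study document due to be kept. On the reading that shredding follows the 6 years, the sentence duplicates the last one. Completion is undefined, and the nearest use of the idea concerns participants who finish at the 3-month data collection. The repair would take one sentence and add no burden, because 6 years is already promised.

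Most of this stands as a comment on drafting: the sentences do not agree, and the text does not say which medium is shredded or when. The step to lost outcome data does not stand. It needs a reader to apply a word for paper disposal to a database, ignore the two sentences that follow, and do so before the analysis is finished. The 3-month wording concerns individual participants and does not define the end of the study. Redundancy is also an ordinary feature of an ethics-board form and weak evidence that an early purge of the database was intended.

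**Conclusion.** The inconsistency is real but clerical, and no change to the plan follows. The sentence concerns records disposal in a confidentiality section. It does not touch randomisation, measurement, estimation or error control, so rewording it would leave sample size, power, bias and the trial's conclusions where they are. The most that could be lost is the ability to audit or re-score the questionnaires of 48 dyads after the study has ended, and only if the sentence were applied to the electronic records.

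This rests on two assumptions. First, shredding refers to paper, or to eventual disposal; the electronic mode of collection and the section's closing sentence both support this. Second, nobody disposes of data before the analysis is done; the Protocol does not say so in terms, but nothing in it suggests otherwise. Staff faced with the two sentences can satisfy the retention promise by keeping the electronic questionnaire data for the 6 years, which is what sensible practice would do anyway.

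### A single fixed block size of 4 leaves an avoidable, conditional opening for selection bias: at most an expected 16 of 48 assignments could be certain in advance, about 4 or fewer under some plausible staffing

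*Protocol*

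**What the plan says.** Under the randomization heading, the protocol assigns 24 adolescent-caregiver dyads to the text-messaging intervention and 24 to attention control. It states: "A computer program will generate the randomization scheme in 12 blocks of 4". No other block size and no stratification is described. The arm is released late: after "consent/assent is obtained, and the participants have completed baseline data, the RA will reveal to which condition he/she was assigned".

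The section on surveys, interviews and questionnaires gives the RA further tasks. For adolescents in the intervention arm, "the RA will instruct them to use the following empirically-validated exercises to induce positive affect". The surveys are also the RA's job: "A trained RA (Master's or Bachelor's level) will administer the survey to the participants". An RA therefore knows the arm of each dyad he or she has handled.

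The protocol does not say how many RAs there are, whether they share allocations, who approaches or schedules families, or whether those people know the block size. A 2:2 split within each block is not stated; it is the natural reading of 24:24 in blocks of 4.

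**The concern.** Releasing the arm only after consent/assent and baseline conceals the current list entry. It does not stop someone from working out the next entry from earlier ones. With 2:2 blocks of a known size, the fourth assignment is always determined, and the third is determined whenever the first two match.

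A person who can make that deduction, and who also influences which family is approached or when, could place more promising families in one arm. The arms would then differ at entry. Outcomes such as self-care and number of glucose checks plausibly depend on motivation, which the baseline measures may not capture, and with 24 dyads per arm a few steered families matter.

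**Working it through.** **Inputs from the protocol.** 12 blocks of 4; 24 and 24 dyads; reveal by the RA after consent/assent and baseline. Check: 12 × 4 = 48 = 24 + 24, so the stated scheme is consistent.

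**Assumptions.** 2:2 within each block; the person deducing knows the block size and the position in the list. The staffing scenarios below are assumed.

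**Upper case: all earlier allocations known.** The six equally likely orders of a 2:2 block contain these numbers of certain assignments: AABB 2, ABAB 1, ABBA 1, BAAB 1, BABA 1, BBAA 2.
- Mean per block: 8/6 = 4/3. Over 12 blocks: 12 × 4/3 = 16 of 48 (33%).
- Distribution: 12 + Binomial(12, 1/3), so the range is 12 to 24 and the central 95% range is 13 to 19.
- Best-guess accuracy by position: 1/2, 2/3, 2/3, 1. The sum is 17/6 per block, and (17/6)/4 = 70.8%.

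**When knowledge is incomplete** (same enumeration):

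| Situation | Expected certain, of 48 |
|---|---|
| Previous reveal pending in 25% / 50% / 75% of cases | 13 / 10 / 7 |
| Previous reveal always pending | 4 (best guess 58.3%) |
| Two reveals always pending | 0 (best guess 54.2%) |
| Two RAs, not sharing, equal random shares | 4 |
| Two RAs, not sharing, 60/40, 70/30, 80/20, 90/10 | 4.5, 5.9, 8.3, 11.7 |
| Three RAs, not sharing, equal shares | 1.8 |
| Two RAs alternating strictly, not sharing | 0 |

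**What it could do to a comparison.** The steering sizes are assumptions, not protocol figures. Suppose k assignments are deducible, half in each arm, and families in those slots are shifted by s SD, with no baseline adjustment. Steering in one arm's slots only gives an arm difference d = s × k/48. Steering up in one arm and down in the other gives d = s × 2k/48. The rejection rate of a two-sided 5% t-test comes from the noncentral t with 46 df and noncentrality d × √12.

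| k | s | One arm: d, rejection | Two-way: d, rejection |
|---|---|---|---|
| 16 | 0.10 | 0.033 SD, 5.15% | 0.067 SD, 5.59% |
| 16 | 0.25 | 0.083 SD, 5.92% | 0.167 SD, 8.74% |
| 16 | 0.50 | 0.167 SD, 8.74% | 0.333 SD, 20.45% |
| 4 | 0.25 | 0.021 SD, 5.06% | 0.042 SD, 5.23% |

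**Effect of varied blocks.** Sizes 4, 6 and 8 in random order, summing to 48, were simulated with a guesser who knows the set of sizes and the full history. Depending on how the sizes are drawn and whether the total of 48 is used, 0.8 to 2.6 of 48 assignments are certain, against 16. Best-guess accuracy is 68.1% to 68.7%, against 70.8%.
- Share of the guessing advantage that remains: from (68.1 − 50)/(70.8 − 50) = 87% to (68.7 − 50)/(70.8 − 50) = 90%.
- With one reveal always pending, accuracy is about 59.5% against 58.3% for fixed blocks. With two pending it is about 56% against 54.2%.

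**The case against.** Blocks of 4 are a conventional choice for 48 dyads, and nothing in the protocol is contradictory or miscalculated here. The list is computer-generated, and release after consent/assent and baseline is a real safeguard: no family consents, and no baseline questionnaire is completed, with the arm disclosed. Custody of the list and withholding of block sizes are often set out in a separate procedure or an analysis plan, and none is at hand. All of this stands, and silence on those matters is not counted as a fault. What is counted is that the protocol itself fixes one block size in writing while giving an RA knowledge of past arms.

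A second objection is that varied blocks barely reduce guessing. This also stands. If staff steered two-way on best guesses at 0.25 SD, the arm difference 2 × 0.25 × (2p − 1) would be 0.21 SD with fixed blocks (p = 70.8%) and 0.18 to 0.19 SD with sizes 4, 6 and 8. Varied blocks work against certain deduction only, and are slightly more guessable than fixed blocks once reveals overlap. Changing the block sizes without withholding information would achieve little.

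A reader might infer that the RA recruits families, that a third of allocations will be known in advance, or that selection bias is present. The protocol supports none of these. It says the RA reveals the arm and teaches the exercises, not that the RA chooses or schedules families. A third is the upper case, and an opportunity is not an occurrence. Nor is 4 of 48 a general ceiling when RAs do not share or reveals overlap: it needs equal shares or a constant lag.

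**Conclusion.** The point holds as a conditional weakness in a stated design choice that should be improved, with medium confidence. The figure of 16 of 48 is exact, but only if staff who recruit or schedule know the block size, the position and all earlier allocations, and each reveal is complete before the next approach. Harm further requires that they act on this.

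With all 16 exploited, steering of 0.25 SD would raise the false-positive rate from 5% to 5.9% (one arm) or 8.7% (two-way); 20% needs 0.5 SD of two-way steering in every deducible slot. With about 4 deducible, 0.25 SD of steering gives at most 5.2%, which is negligible. Baseline adjustment would reduce bias from steering on measured prognosis, but not on unmeasured motivation.

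**What to change.** Replace the sentence on blocks with wording such as:

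*The list will be computer-generated, 24:24, in permuted blocks of varying size in random order. The block sizes, the list and, where existing staffing allows, the running allocation record are withheld from staff who recruit or schedule families.*

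Keep the present release after consent/assent and baseline. Sizes 4, 6 and 8 would serve, for example 2 × 4 + 4 × 6 + 2 × 8 = 48, recorded somewhere that recruiting staff do not see. The two halves belong together: varied sizes remove most certain predictions, while withholding the running record removes the basis for guessing.

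**Cost.** One sentence and a regenerated list, still 24:24, with roles separated only as far as existing staff allow. If enrolment has begun, which the protocol does not say, apply the change only to unused blocks. If enrolment stops early, the arms could differ by 4 dyads, where fixed blocks of 4 allow at most 2. In simulation at stopping points from 24 to 42 dyads, this had a probability of at most about 0.4%.

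### Does sending the SMS affect surveys in the same weeks as the intervention arm's gift codes make them misrepresent affect over weeks 1-8?

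*Protocol*

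**What the plan says.** All the relevant text is in the Protocol, under Surveys, Interviews, and Questionnaires.

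- **Gifts (item 4 of the intervention list).** "For those in the Text-Messaging Condition, an Amazon gift card" worth $5 is provided, and "the redemption code will be sent via SMS to participants". On timing: "Gifts will be sent every 2 weeks for 8 weeks (Weeks 2, 4, 6, 8". Items 1 to 4 follow a sentence that introduces them as ways to raise positive affect.
- **SMS affect survey, both arms.** "on weeks 2, 4, 6, 8, the Positive Affect Negative Affect Scale - Children (Brief Version) will be administered by SMS".
- **Recall.** In the description of the PANAS-C, respondents rate "the extent to which they have experienced each particular emotion within the last week".
- **Contact times.** "adolescents in all conditions will be asked the best days/times to contact them". The stated reason is to make participation more likely.
- **Clinic assessment.** The PANAS-C is also part of the iPad survey given "in a private space at each of the follow-up visits", and "an exit interview and evaluation will be administered at the final data collection (3 months".

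The Protocol does not give the day within the week for the code or the survey, or which comes first. It names no analysis of the SMS surveys and no average over weeks 1-8.

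**The concern.** Every SMS survey falls in a week when one arm receives a gift and the other does not (4 of 4 survey weeks, against 4 of the 8 weeks overall). The survey measures affect, which the gift is meant to lift. Survey and gift share a two-week period, so repeating the survey need not average out the point in the cycle at which it lands.

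With a one-week recall, a survey just before a code would describe a gift-free week. One sent six days after a code would describe a week made up wholly of post-gift days. If reactions to the gift fade quickly, the difference between arms could look larger or smaller than it was over the whole eight weeks, and a reader could not tell which. These four surveys are 4 of the 5 post-baseline PANAS-C assessments that the document names.

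**Working it through.** There is no figure in the plan to reproduce. The check asks what the surveys are meant to measure, then how large a departure could be.

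**1. Target.** The Protocol says that the PANAS-C measures affect over the last week. It sets no eight-week average as a quantity of interest. For the week actually recalled, comparing randomised arms on one common schedule is valid, and an effect of the gift is part of the effect of the assigned intervention.

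**2. Inputs for the size.** Code and survey fall in the same week (Protocol). Recall is taken as the 7 days ending on the survey day. A gift is assumed to add g points for L days from the code day. Neither g nor L is in the document.

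**3. One-day effect (L = 1).** Share of weeks 1-8 affected: 4/56 = 0.071. Share of recalled days: 4/28 = 0.143 if the survey is on or after the code day, and 0/28 = 0 if before. The departure is 0.143 - 0.071 = +0.071 or 0 - 0.071 = -0.071, that is, about 0.07g in either direction.

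**4. Seven-day effect (L = 7).** Let d = survey day minus code day. There are 7 - |d| day pairs for each d, 49 in all. In weeks 4, 6 and 8 the number k of recalled days in a post-gift week is d + 1 for d ≥ 0, and |d| - 1 for d < 0 (carried over from the previous code). Against the 14-day cycle share of 7/14, the departure is (k/7 - 0.5)g.

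| d | pairs | k | departure |
|---|---|---|---|
| -6 | 1 | 5 | +0.21g |
| -5 | 2 | 4 | +0.07g |
| -4 | 3 | 3 | -0.07g |
| -3 | 4 | 2 | -0.21g |
| -2 | 5 | 1 | -0.36g |
| -1 | 6 | 0 | -0.50g |
| 0 | 7 | 1 | -0.36g |
| +1 | 6 | 2 | -0.21g |
| +2 | 5 | 3 | -0.07g |
| +3 | 4 | 4 | +0.07g |
| +4 | 3 | 5 | +0.21g |
| +5 | 2 | 6 | +0.36g |
| +6 | 1 | 7 | +0.50g |

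The extremes of 0.5g appear only here. Order does not fix the sign: with the gift first, 6 + 5 = 11 of 21 pairs understate; with the survey first, 1 + 2 = 3 of 21 overstate. In all, 36 pairs understate and 13 overstate. The rule that gift first overstates and survey first understates fits a very short effect, whose departure is one-seventh of 0.5g (0.071/0.5).

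**5. Benchmark.** The cycle share of 0.50 is not the weeks 1-8 share, because no code precedes week 2. With codes on the first day of the week the latter is 28/56 = 0.50; on the seventh day it is (7 + 7 + 7 + 1)/56 = 0.39.

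**6. Would another timing be clearly better?** Take two surveys six days after codes 1 and 3, and two on the day before codes 2 and 4. With codes on days 8, 22, 36 and 50, the surveys fall on days 14, 21, 42 and 49. They recall days 8-21 and 36-49, which is 28 of 56 days, the most that four one-week recalls can cover in any case. Days 22-35 and 50-56 are never sampled, and the roughly two-week spacing becomes 7, 21 and 7 days.

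**7. Clinic PANAS-C.** The last code falls on day 50-56. Taking 3 months as day 84-91, the gap is 84 - 56 = 28 to 91 - 50 = 41 days.

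**The case for a change.** The strongest opposing case is that send times belong in a protocol, and that no analysis plan can recover days that were never asked about. Gifts are the only component with a stated two-week cycle, so a survey locked to the same period samples one phase of it. Preferred contact times might make that phase differ between participants. Nor would such scatter cancel out: with all 49 pairs weighted equally and a seven-day effect, mean coverage in weeks 4, 6 and 8 is 119/343 = 0.35, not 0.50.

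The facts in this stand: identical weeks, gifts in one arm, no stated order. So does the practical remark that writing down the day and order would help whoever reads the SMS results.

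The inference does not follow. The 0.35 depends on an assumed seven-day effect and on equal weights that nothing in the document supports. The question about contact times is put to both arms to aid participation and is not said to set the day of either message. If it did, both texts could go on the same preferred day, in a constant order. Measuring affect in weeks when a component is delivered is a defensible choice, and nothing in the text is contradicted or misstated by it.

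**Conclusion.** The concern does not hold. The overlap of weeks is real, but it threatens no outcome or conclusion that the Protocol states. The gift belongs to the intervention, the randomised comparison is valid for the week recalled, and an average over weeks 1-8 is not a stated target. Were it one, the departure would be about 0.07g for a one-day effect. It could reach 0.5g only if the effect stayed constant for seven days, with the sign open and g unknown. Alternative timing trades even spacing for different gaps without covering more days.

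This rests on reading the recall as seven days ending on the survey day and on the SMS surveys having no stated eight-week estimand. If results were later presented as average affect over weeks 1-8, the caveat would apply to that claim. The 3-month clinic assessment, 28 to 41 days after the last code, is untouched.
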